#### 7.1.3.2 *Imputation of missing or partial dates of AE end dates*

If the event is indicated as ongoing at the end of the study, no imputation is needed.

If the event is not indicated as ongoing:

- Month/year available and day missing:
  - Use the last day of the month to impute the AE end date. If the imputed end date is before the AE start date, keep the end date same as the start date. If the subject died, use the date of death to impute the end date.
- Year available and month/day missing:
  - If the year is the same as or before the year of the last dose in Part 2, set the end date as December 31.
  - If the year is after the year of the last dose in Part 2, set the end date as January 1.

- Year/month/day all missing:
  - Impute the end date as December 31 of the Part 2 last dose year. If the imputed end date is before the AE start date, keep the end date same as the start date. If the subject died, use the date of death to impute the end date.

#### 7.1.4 Conventions for Missing Concomitant Medication Dates

Concomitant medications with completely or partially missing will be imputed as follows.

##### 7.1.4.1 *Imputation of missing or partial dates of concomitant medication start dates*

- Month/year available and day missing:
  - The first day of the month will be used for the start date.
- Year available and month/day missing:
  - Set the start date as January 1.
- Year/month/day all missing:
  - If date of birth is available, use the date of birth as the start date.
  - If date of birth is not available, estimate date of birth using the screening date and age, and use the estimated date of birth as the start date.

##### 7.1.4.2 *Imputation of missing or partial dates of concomitant medication end dates*

If the concomitant medication is indicated as ongoing, no imputation is needed.

If the concomitant medication is not indicated as ongoing, use the same algorithm in Section 7.1.3.2 to impute.

#### 7.1.5 Conventions for Missing Data

There will be no imputation of incomplete or missing data.

Plasma concentrations that are below the limit of quantification (BLQ) will be treated as zero in the summarization of concentration values. These values will be flagged in the data listings and deviations from this convention may be considered on a case-by-case basis as deemed appropriate.

## 7.2 Analysis Sets

The randomized set will include all subjects who were randomly assigned to planned treatment through the IVRS/IWRS.

The PK analysis set for Parts 1 and 2 will include all subjects who received at least 1 dose of study drug and have at least 1 post-dose measurable TAK-935 or M-I plasma concentration.

CCI

The full analysis set (FAS) for Parts 1 and 2 will include all subjects who were randomized, received at least 1 dose of study drug, and have at least 1 valid post-baseline value for assessment of the efficacy endpoint(s) in Part 1 or Part 2. In FAS efficacy summaries, subjects will be analyzed according to the treatment to which they were randomized.

The safety analysis set for Parts 1 and 2 will include all subjects who received at least 1 dose of study drug. In safety summaries, subjects will be analyzed according to the actual treatment they received.

### 7.3 Disposition of Subjects

Study information will be presented, including date first subject signed the Informed Consent Form, date of last subject's last visit/contact, date of last subject's last procedure for collection of data for primary endpoint, Medical Dictionary for Regulatory Activities (MedDRA) Version, World Health Organization Drug Dictionary Version (WHODRUG), and SAS Version.

Disposition of all screened subjects (denominator) will be tabulated (count and percent); there will be no inferential analysis of subject disposition data.

The number and percentage of subjects who complete study drug and all study visits in Part 1 of the study, prematurely discontinue study drug and study visits in Part 1 will be summarized by treatment group and overall for all randomized subjects in the double-blind period. For all the subjects who continue in Part 2 of the study, the number and percentage of subjects who complete study drug and all study visits in Part 2, prematurely discontinue study drug and study visits in Part 2 will be summarized. For each of Part 1 and Part 2, the primary reason for discontinuation of study drug/visits, as entered on the electronic case report form (eCRF), will be tabulated. The date of first dose, date of last dose, duration of treatment and the reason for premature discontinuation of study drug/study visit will be presented for each subject in listings. Disposition of screen failure subjects in Part 1 will be summarized descriptively. Primary reasons for failure will be summarized and will be presented in a data listing

The number and percentage of subjects who comprised each analysis set will be summarized by treatment group and overall in Part 1, and overall in Part 2, respectively.

Disposition of the study drug dose combination for subjects in Part 1 and 2 will also be summarized by sequence of dose. For example, for subjects taking TAK-935 in Part 1, the number and percentage of subjects with dose combination of 100 to 200mg BID will be summarized. This summary will be based on safety analysis set. Details for important (significant) protocol deviations will be provided in a data listing.

### 7.4 Demographic and Other Baseline Characteristics

Demographic and baseline characteristics (e.g., date of birth, sex, Hispanic ethnicity, race as described by the subject, epilepsy diagnosis) will be summarized and listed for subjects by treatment group and overall using the safety analysis set in Part 1. Summary statistics (number of

subjects, mean, SD, median, minimum, and maximum) will be presented for continuous variables (e.g., age, and weight), and the number and percentage of subjects within each category will be presented for categorical variables (e.g., sex, ethnicity, race). No inferential statistics will be presented. Individual subject demographic and baseline characteristic data will be listed.

Demographic variables of screen failure subjects and reasons for screen failure will be summarized overall for subjects who are screened but not enrolled in the study. Individual demographic characteristics, date of informed consent, any available safety data and reason for screen failure will also be presented in the data listing.

### **7.5 Medical History and Concurrent Medical Conditions**

Medical history refers to the significant conditions or diseases relevant to the disease under study that resolved at or prior to signing of informed consent. Concurrent medical conditions are those significant ongoing conditions or diseases present at signing of informed consent.

Medical history, epilepsy diagnosis, and concurrent medical conditions will be coded using the latest version of Medical Dictionary for Regulatory Activities (MedDRA, version 19.0) and will be summarized by treatment group and overall in Part 1, using System Organ Class (SOC) and MedDRA preferred term. The table will include number and percentages of subjects and will be sorted in alphabetical order by system organ class and preferred term. A subject will only be counted once within a particular class even if he/she has multiple conditions/symptoms. Summaries will be presented for Part 1 only, and will be based on the safety analysis set for Part 1.

All medical history, epilepsy diagnosis, and concurrent medical condition data will be presented in listing.

### **7.6 Medication History and Concomitant Medications**

Medication history information to be obtained includes any medication relevant to eligibility criteria and the efficacy or safety evaluations stopped at or within 28 days before signing of informed consent. AED history will be collected as part of the medication history information. Medications used from signing of informed consent through the end of each study part will be considered as concomitant medications for each study part, respectively.

Summaries of medication history will be presented for Part 1 and Part 2, separately, and will be based on the safety analysis set for Part 1. Concomitant medications that started and stopped prior to baseline, started prior to baseline and ongoing at baseline, started after baseline, and ongoing at baseline and started after baseline will be summarized using the safety analysis set in Part 1. Concomitant medication for Part 1 is defined as the medication that the patient started taking before first dose in Part 1 and ongoing in Part 1 of the study, and concomitant for Part 2 is defined as the medication that the patient started taking before first dose in Part 2 and ongoing in Part 2. No inferential statistics will be presented.

All prior and concomitant medications data will be presented in listing.

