##### 8.1.1.2 Rescue Medication

Rescue medication will be used in case of major seizures, according with the judgment of the investigator and based on evidence of prior positive responses of each subject. Rescue medication will not be supplied by the sponsor.

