**9.1.9 Documentation of Concomitant Medications**

Concomitant medication is any drug given in addition to the study drug. These may be prescribed by a physician or obtained by the subject over the counter. Concomitant medication is not provided by Takeda. At each study visit, subjects will be asked whether they have taken any medication other than the study drug (used from signing of informed consent through the end of the study), and all medication including vitamin supplements, over-the-counter medications, and oral herbal preparations, must be recorded in the source document and eCRF. Documentation will include generic medication name, dose, unit, frequency, route of administration, start and end dates, and reason for use.

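### SAP 7.6 defines concomitant medication by study part in two conflicting ways: one carries earlier drugs into Part 2, the other omits every drug started after the part's first dose

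*SAP*

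**What the plan says.** SAP 7.6 opens with a broad rule: "Medications used from signing of informed consent through the end of each study part will be considered as concomitant medications" for each study part. The window starts at consent for both parts.

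The next paragraph promises summaries. Besides drugs that were both started and stopped before baseline, it says that medications that "started prior to baseline and ongoing at baseline, started after baseline, and ongoing at baseline and started after baseline will be summarized", using the Part 1 safety analysis set.

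The same paragraph then gives a second, narrower rule. For Part 1, concomitant means "medication that the patient started taking before first dose in Part 1 and ongoing in Part 1 of the study"; for Part 2 it means "medication that the patient started taking before first dose in Part 2 and ongoing in Part 2". The section closes with "All prior and concomitant medications data will be presented in listing".

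Protocol 9.1.9 sets no start-date condition: "Concomitant medication is any drug given in addition to the study drug", recorded when "used from signing of informed consent through the end of the study". Protocol 8.1.1.2 expects on-treatment use: "Rescue medication will be used in case of major seizures". SAP 7.12, which lists changes, does not address the definition.

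**The concern.** Two programmers following SAP 7.6 could produce different by-part summaries, and each could point to a sentence in support. Neither rule picks out the drugs actually taken during a part.

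Background AEDs are meant to stay stable (Protocol 7.1), so additions after the first dose are the informative rows: rescue treatment, a new AED, or treatment of an adverse event. The second rule drops these from the part in which they begin. The first repeats drugs in Part 2 that were no longer being taken.

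The groups are small. With the planned 16 TAK-935 and 4 placebo subjects as denominators, reclassifying one subject moves a Part 1 percentage by 1/16 = 6.25 points or 1/4 = 25 points.

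**Working it through.** There is no planned figure to reproduce, so the check writes each rule as a date condition and compares it with actual use.

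**Notation.** A drug starts on day s and stops on day e. C is consent; F and E are the first dose and the end of the part.

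- First rule: s ≤ E and e ≥ C.
- Second rule: s < F and e ≥ F.
- Actual use during the part: s ≤ E and e ≥ F.

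**How the rules relate.** Because F ≤ E and C < F, every drug meeting the second rule also meets the first, so the second is nested in the first. A day-by-day grid of start and stop dates found no exception. Actual use lies between them: it combines the first rule's start condition with the second rule's stop condition.

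**Timeline (assumed for illustration, built on the visit schedule).** Consent Day -28; Part 1 from Day 1 to Day 30; Part 2 from Day 31 to Day 90. The representative days were Day -60 (before consent), -10 (baseline), 15 (Part 1), 50 (Part 2) and 120 (after dosing). Pairing start and stop periods, with some use after consent, gives 13 patterns:

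| Course | Patterns | First rule counts in | Second rule counts in | Taken during dosing in |
|---|---|---|---|---|
| Starts before consent or in baseline, stops in baseline | 2 | both | neither | neither |
| Starts before consent or in baseline, stops in Part 1 | 2 | both | Part 1 | Part 1 |
| Starts before consent or in baseline, stops in Part 2 or later | 4 | both | both | both |
| Starts and stops in Part 1 | 1 | both | neither | Part 1 |
| Starts in Part 1, stops in Part 2 or later | 2 | both | Part 2 | both |
| Starts in Part 2, stops in Part 2 or later | 2 | Part 2 | neither | Part 2 |

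**Result.**
- First rule: right in 4 + 2 + 2 = 8 patterns, wrong in 2 + 2 + 1 = 5. Every error is an over-count, and all five include a false Part 2 entry.
- Second rule: right in 2 + 2 + 4 = 8, wrong in 1 + 2 + 2 = 5. Every error is an omission from the part in which the drug started. These five are all the patterns that start after the first Part 1 dose.
- Only the course confined to Part 1 is wrong under both rules.

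**Conflict inside the section.** For Part 1, a drug started after baseline cannot meet the second rule. Nor can one started and stopped before baseline. Two of the promised categories would therefore be empty by construction if that rule governed.

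**The case against.** The strongest reply is that little is lost. All medications are listed, Protocol 9.1.9 records start and end dates and reason for use, and with about 20 subjects every rescue or new drug can be found. The summaries carry no inferential statistics, and the TEAE definitions in SAP 7.11.1 do not refer to concomitant medication. All of this stands and limits the point to descriptive summaries. It does not make those summaries reproducible.

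Several stronger readings are tempting but not supported:

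- **That the definitions are opposites.** They are nested: one is too wide, the other too narrow.
- **That every new drug is counted in both parts or in none.** This is true only of a course confined to Part 1. The first rule correctly places a drug started in Part 2, and one started in Part 1 and continued.
- **That the category for drugs started after baseline stops at the end of Part 1.** The Part 1 safety analysis set is a population, not a date limit. Subjects enter Part 2 only after completing Part 1, so the category can include drugs started in Part 2. What it lacks is a split by part.
- **That counting screening-only drugs in Part 1 is plainly an error.** They fall within the protocol's collection window and have their own SAP category. The clear over-count is carrying them into Part 2.
- **That seizure results are affected.** The exploratory efficacy section is redacted, so how it handles rescue medication cannot be judged.

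**Conclusion.** The concern holds as a conflict between two stated rules, neither of which gives a correct by-part classification. The first over-counts, chiefly by bringing drugs already stopped into Part 2. The second omits all starts after the part's first dose and disagrees with both its own section and Protocol 9.1.9.

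The counts of 5 in 13 describe kinds of course, not expected frequencies; the documents give no rate of rescue or new-drug use, so the number of subjects affected is unknown. The result takes use between a part's first dose and its end as the standard. It depends on the order of the dates, not on the particular days chosen, except for drugs started during de-escalation or follow-up, whose part the section does not settle.

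A reader might infer that on-treatment drugs vanish from the report or that the primary endpoint is compromised. Neither follows. The point is worth correcting because the rule as written gives wrong summaries and the correction is cheap.

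**What to change.** Replace both sentences in SAP 7.6 with one overlap rule: a drug is concomitant for a part if it was taken on at least one day from that part's first dose to the end of that part, whatever its start date. On the 13 patterns this reproduces the last column of the table.

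State the end of each part:

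- For subjects who continue, Part 1 ends at the first open-label dose.
- For subjects who do not enter Part 2, say whether the de-escalation and 30-day follow-up after their Final Visit are included.
- For Part 2, say the same. SAP 4.4 lists both periods under Part 2, but SAP 7.6 does not say whether they count here.

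Keep drugs used after consent but stopped before the first Part 1 dose in the existing category for drugs started and stopped before baseline, and do not count them as on-treatment in either part. This stays within the protocol's collection window. For each part, show separately the drugs ongoing at first dose and those started during the part. That split will depend on the start-date imputation in SAP 7.1.4.1, so imputed dates should be flagged.

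The cost is a wording change in the SAP and one date condition in programming. No new data are needed.

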## 7.7 Study Drug Exposure and Compliance

The date and time of each dose for each subject will be reported in a data listing based on the safety analysis set. Summaries of study drug concentration and exposure data will be provided by dose using the safety analysis set in Parts 1 and 2 separately. No inferential statistics will be presented.

The duration of exposure (days) to the double-blind study medication in Part 1 is defined as (date of last dose of double-blind study drug - date of first dose double-blind study drug + 1). The duration of exposure to the open-label study medication in Part 2 is defined as (date of last dose of open-label study drug – date of first dose of open-label study drug + 1). For patients who have been treated in both Parts 1 and 2 with active drug (TAK-935), the duration of exposure to the TAK-935 overall is defined as (date of last dose of open-label study drug – date of first dose of double-blind study drug +1).

The date of last dose of study drug will be obtained from the eCRF. In the event that the date of last dose is missing, then for analysis and summary purpose, the last dose date will be estimated as the later date between the last drug dispense date plus the number of days in the dosing interval (dispense date + (next visit day – last visit day) + 1) and the last study visit day.

The duration of double-blind treatment in Part 1 will be summarized by treatment group using the following categories: 1 to 11 days and 12 to 21 days, 22 to 31 days. The duration of open-label treatment in Part 2 will be summarized using the following categories: 32 to 41 days, 42 to 85 days, and 85 days or more. The intervals are calculated using the actual study days according to the visit window definitions in [Table 7.a](#) and [Table 7.b](#).

In Part 1 of the study, subjects are to take 1-3 tablets for TAK-935 (100mg/200mg/300mg) or matching placebo twice each day. In Part 2, subjects are to take 1-3 tablets for TAK-935 (100mg/200mg/300mg) twice daily. Overall percent study drug compliance for each period (Part 1 and Part 2) will be calculated as:

$$\text{Overall compliance (\%)} = 100 \times \{(\text{number of tablets dispensed} - \text{number of tablets returned}) / (\text{expected number of tablets to be taken})\},$$

where expected number of tablets to be taken = [number of tablets to be taken daily\*(date of last dose of medication – date of first dose of medication + 1)].

Compliance will be presented to 1 decimal place in the derived dataset and Table, Figures, and Listings (TFLs) outputs.

Overall study drug compliance in Part 1 and Part 2 will each be summarized using descriptive statistics and by the number of subjects in each of the following compliance categories: <70%, >=70 to <=130%, >130%, and missing, if applicable.

All study drug administration (double-blind placebo in Part 1, double-blind active (TAK-935) drug in Part 1, and open-label study drug in Part 2) and accountability data will be listed by site and subject number. The following variables will be listed: subject identifier, treatment, first and last double-blind dose dates, first and last open-label dose dates, number of tablets dispensed and

returned, overall double-blind percent compliance in Part 1, and overall open-label study drug percent compliance in Part 2.

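### SAP 7.7: the Part 2 duration categories count Day 85 twice and omit Day 31, and the missing-last-dose rule overshoots the scheduled last dose and can land on an off-drug visit

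*SAP*

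**What the plan says.** All the rules are in SAP 7.7.

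- **Part 2 categories:** "32 to 41 days, 42 to 85 days, and 85 days or more". **Part 1 categories:** "1 to 11 days and 12 to 21 days, 22 to 31 days".
- **Scale:** "The intervals are calculated using the actual study days according to the visit window definitions in" Tables 7.a and 7.b.
- **Defined duration:** "The duration of exposure to the open-label study medication in Part 2 is defined as" the last open-label dose date minus the first, plus 1.
- **Missing last-dose date:** the later of two dates, the formula ending "dispense date + (next visit day – last visit day) + 1) and the last study visit day".
- **Compliance:** tablets used divided by tablets expected, "where expected number of tablets to be taken = [number of tablets to be taken daily" multiplied by the days from first to last dose. Results are grouped as "<70%, >=70 to <=130%, >130%, and missing, if applicable".

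The dosing calendar is in SAP 4.4. Open-label dosing starts on Day 31 and the Final Visit is on Day 85. De-escalation runs to Day 90 from 300 mg BID or to Day 87 from 200 mg BID, and there is none from 100 mg BID. Visits 8 and 9 (Days 91 and 121) come after the last dose.

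**The concern.** A set of duration categories should give every treated subject exactly one place. This set does not, and its labels describe study days while the quantity defined beside them is a length of exposure. Two programmers following the section could produce different tables.

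The rule for a missing date matters a little more, because the last-dose date is used elsewhere. It sets the 7-day limit for laboratory, vital-sign and ECG tables (SAP 7.11.2 to 7.11.4) and the end of the treatment-emergent window (SAP 7.11.1), on which the primary endpoint rests. An estimate that is too late lengthens exposure and stretches both windows into off-drug time.

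**Working it through.** **Reproducing the stated length.** From SAP 4.4, a 300 mg BID completer takes the first open-label dose on Day 31 and the last on Day 90: 90 − 31 + 1 = 60 = 10 + 44 + 6 days. This agrees with the approximately 60 days in the Protocol Study Summary. The duration definition itself is therefore sound.

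**Categories on study days.**
- Day 85 meets both 42 to 85 and 85 or more.
- A last open-label dose on Day 31 meets none. With the ±2-day window in Protocol Appendix A, Visit 5 may fall on Day 29 or 30, and a last dose on either of those days also meets none.
- Visit 5 on Day 33 is also permitted. The last double-blind dose is then on Day 32, above the Part 1 limit of 31 if raw study days are used.

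**Categories on the defined duration.**
- 300 mg BID: 60 days. 200 mg BID: 87 − 31 + 1 = 57. 100 mg BID: 54 or 55, for a last dose on Day 84 or 85.
- Longest on schedule: Visit 5 on Day 29, Visit 7 on Day 87, six taper days (87 to 92), so 92 − 29 + 1 = 64.
- All completers therefore fall in 42 to 85, the top category is empty, and 1 to 31 days has no category.

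**Missing last-dose date.** Let drug be dispensed at visit day v, with the next visit on day n. The formula gives v + (n − v) + 1 = n + 1, the day after the next visit. Scheduled dosing at each step ends on day n − 1. Visit 8 is taken as the next visit after Day 85.

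| Dispensed | Next visit | Formula | Scheduled last day | Days late |
|---|---|---|---|---|
| 1 | 11 | 12 | 10 | 2 |
| 11 | 21 | 22 | 20 | 2 |
| 21 | 31 | 32 | 30 | 2 |
| 31 | 41 | 42 | 40 | 2 |
| 41 | 85 | 86 | 84 | 2 |
| 85 (300 mg BID taper) | 91 | 92 | 90 | 2 |
| 85 (200 mg BID taper) | 91 | 92 | 87 | 5 |

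The Day 32 result for Part 1 falls after the nominal first open-label dose on Day 31.

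**The last-visit alternative.** Nothing limits it to on-treatment visits, and Protocol 9.3.7 requires the Follow-up Visit of all subjects, including early withdrawals. For a 300 mg BID completer seen on Day 121, the estimate is Day 121: 121 − 90 = 31 days late, and 121 − 31 + 1 = 91 days of exposure instead of 60.

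**Knock-on effects of a Day 121 estimate.**
- The 7-day limit moves from 90 + 7 = 97 to 121 + 7 = 128. Of the assessments under this limit, Appendix A schedules only vital signs on Day 121.
- The treatment-emergent window closes at last dose + 29: Day 119 for a Day 90 last dose, Day 116 for Day 87. Collection stops at Visit 9, so the gain is 121 − 119 = 2 days or 121 − 116 = 5 days.

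**Compliance.** Summed day by day, expected tablets for the planned path are 10×2 + 10×4 + 10×6 = 120 in Part 1 and 10×4 + 44×6 + 3×4 + 3×2 = 322 in Part 2. A perfect taker scores 100% in both.

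**The case against.** **The visit-window sentence.** SAP 7.7 ties the intervals to Tables 7.a and 7.b. If each day is first mapped to a visit, Days 30 and 32 both belong to Visit 5 (27–36), Days 40 and 42 to Visit 6 (up to 53), and so on. On that reading the late Part 1 dose on Day 32 has a category, and the 2-day overshoot changes none. A reader might infer that the overshoot moves subjects to another category at most dispensing visits; the documents do not settle this, so it is not claimed. But the mapping is not written out, and the cut-offs 41 and 85 are scheduled visit days, not window limits. It also leaves Day 85 in two categories, and Table 7.b gives the first open-label dose day no window except baseline.

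**Late visits.** If the next visit is held 2 days late, dosing until the day before ends on Day 12, 22, 32, 42 or 86, which the formula returns when it uses scheduled days. The overshoot is therefore a statement about the nominal schedule. If the formula uses the actual visit day, the 2-day gap returns.

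**Decliners of Part 2.** A reader might infer that a 300 mg BID subject who declines Part 2 and tapers to about Day 36 has no Part 1 category. No passage says whether that taper counts as double-blind exposure, so this is a question to answer and not a demonstrated gap.

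**Safety tables.** SAP 7.1.2 uses the value closest to the scheduled day, so a Visit 7 reading displaces Day 121 and the by-visit table is unchanged. Markedly abnormal summaries already take all observations. This stands, and limits the effect.

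**Compliance.** A reader might infer that the formula misclassifies perfect takers. That needs one fixed daily count, which the SAP does not specify. It describes 1 to 3 tablets by dose level, and the sensible day-by-day reading works.

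**Conclusion.** The point holds as a minor error in descriptive tables. Two faults stand on the text: the Part 2 categories overlap at Day 85 and miss the first open-label day, and they do not match the duration defined beside them. The missing-date rule is 2 days late on the nominal schedule (5 for the 200 mg BID taper) and, through its last-visit alternative, can reach Day 121. That last step assumes that the last study visit means the last one attended, which is the plain reading.

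The consequences are small. The rule applies only when the eCRF date is missing, which should be rare because Protocol 9.1.18.1 has dose times recorded before each scheduled visit. Where it applies, the treatment-emergent window gains 2 days for a Day 90 last dose or 5 for Day 87, and by-visit tables are unchanged when a Visit 7 reading exists. No change to an endpoint estimate has been shown. Compliance is a clarification only; it is not an endpoint and defines no analysis set.

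**What to change.** 1. **Categories.** Label them study day of last dose. Start Part 2 at the first open-label dose day, place Day 85 in one category only, and leave the top Part 1 category open-ended. Report the defined duration separately as a continuous summary. State whether a taper after declining Part 2 counts as Part 1 exposure. Do not read the top Part 2 category as completion: a subject with no de-escalation may have a last dose on Day 84 or 85, or earlier if Visit 7 is early. Take completion from the disposition table (SAP 7.3).
2. **Missing last-dose date.** Use a documented dosing date first (per-dose records, dosing card, phone contact). Otherwise replace + 1 by − 1, which gives Days 10, 20, 30, 40, 84 and 90. Exclude Visits 8 and 9 from the last-visit alternative. Cap the date at the end of the subject's scheduled dosing, including any de-escalation, and for Part 1 before the first open-label dose. The cap also brings the 200 mg BID taper to Day 87. Flag the date as imputed.
3. **Compliance.** State expected tablets as the sum, over dose periods, of assigned tablets per day times days at that dose.

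The cost is SAP wording and programming, plus a check that dose-change dates from the chart and dosing card are in the database. The section already plans the listing needed: "The date and time of each dose for each subject will be reported in a data listing".
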